The sample size formula developed by Donner [64] for stratified randomized trials was employed. From preliminary data we observe that the rate of unplanned all-cause hospitalization during the 1-year follow-up period is 14% across all four large health care systems in standard medical care group. We expect that the hospitalization rate in PIECES group will be 3% lower than that in the standard medical care group. Electronic health records show that the number of patients with coexistent CKD, hypertension and diabetes are 4,419, 4,738, 4,175 and 1,093 in Parkland, Texas Health Resources, ProHealth, and VA North Texas, respectively. The numbers of clinics are 25, 40, 50, and 9 in Parkland, Texas Health Resources, ProHealth, and VA North Texas, respectively. From a preliminary dataset extracted from

Parkland Healthcare System and THR Healthcare System, we obtained an intracluster correlation coefficient (ICC) of 0.015.

If we assumed ICC = 0.015 to detect a 3% difference in the rate of unplanned all-cause hospitalization, a total of 10,991 patients are needed to achieve 80% power at a two-sided 5% significance level. We would need to enroll 3,367, 3,610, 3,181, and 833 patients from Parkland, THR, ProHealth, and VA North Texas, respectively. Here, 10,991 patients are 76.2% of 14,425 patients from the 4 healthcare systems participating in the study. Waiver of consent has been obtained from all IRBs overseeing the study and no informed consent will be obtained from patients. There is an opt-out option available for patients in the implementation and in the control groups and based on the nature of the interventions a small number of opt-out requests is expected. Additional practice sites/ clinics will be available at 3 of the 4 participating health care systems as enrollment sites for additional patients if required in the future.

11.3 Statistical Analysis Plan:

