Standard descriptive analysis will be performed where we summarize continuous variables by mean and standard deviation, and categorical variables by count and percentage. The one-year unplanned all-cause hospitalization rates will be compared using the generalized Mantel-Haenszel procedure as presented by Donner [64], which is suitably adjusted for clustering. Furthermore, we will use generalized linear mixed model (GLMM) to examine if there is a significant difference in hospitalization rates between two intervention groups after controlling for potential confounding patient, clinician and clinic factors. The mixed model includes clinic random effects to account for within-cluster correlation. Univariate mixed models will be employed to assess the marginal association between the outcome and individual covariates. The final multivariate model will include covariates identified by the stepwise variable selection procedure as well as those considered to be clinically important *a priori*. Similar analysis will be performed to compare the rates of disease-specific hospitalization. As secondary analyses, the Kaplan-Meier plots will be generated to explore the difference in time to hospitalization between the two arms. Cox models with frailty will be implemented to evaluate the treatment effect on the event times of hospitalization, CV, and death events, controlling for confounding factors. Random effects for clinics are also included. Similar strategy of univariate and stepwise variable selection procedure in mixed model will be implemented to the Cox models with frailty. Statistical significance will be reported for $p\text{-value} < 0.05$. All statistical analyses are performed using statistical software SAS 9.4 (SAS Institute, NC, Gary).

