To construct and evaluate predictive models for unplanned all-cause hospitalizations, disease-specific hospitalizations, 30-day readmissions, cardiovascular events and deaths, the total cohort will be randomly separated into derivation and validation datasets (2/3 and 1/3 sample, respectively). Based on the derivation set, we will select independent variables with $p\text{-value} < 0.20$ from univariate analysis as candidate variables for multivariate analysis. We will explore possible contributions to models from interactions of independent variables and from splines, transformations, and recursive partitioning for continuous variables. We will use the stepwise variable selection procedure on generalized linear mixed model (GLMM) to identify variables that are significantly associated with outcome variables such as hospitalization, 30 day readmissions, cardiovascular events and deaths. The goodness of fit criteria and the Bayes Information Criterion (BIC) will be used for model selection.

The resulting model will be externally validated based on the validation dataset. We will evaluate calibration through the Hosmer-Lemeshow test; we will measure discrimination by the

c-statistic, the area under the curve (AUC) for the receiver operating characteristic (ROC) curve and by the range of predicted risks. We will divide the patients into five groups based on the quintiles of their predicted risk by the model. We will compare the true event rate among the quintile groups to examine how well the predictive model separate patients at different levels of risk.

12. Source Documents and Access to Source Data/Documents

The main source of data will be through Pieces extraction of patient data from the EHRs of all study sites. Only the PI and study team members who are HIPAA certified will have access to this data. The data will be de-identified before transfer to the statistical team for analysis. Other sources of data is readmission data from the DFW Hospital Council, Pro Health databases and VA of North Texas databases/information.

13. Quality Control and Quality Assurance

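### Section 11.3 calls validation on a random third of the trial's own cohort external; it is internal validation, and the only calibration method named does not estimate miscalibration

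*Combined protocol and SAP*

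**What the plan says.** The predictive-model part of Section 11.3 (Statistical Analysis Plan) sets the split: "the total cohort will be randomly separated into derivation and validation datasets (2/3 and 1/3 sample, respectively". It then labels what the second part is for: "The resulting model will be externally validated based on the validation dataset".

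On performance it says: "We will evaluate calibration through the Hosmer-Lemeshow test". Discrimination is to be measured by the "c-statistic, the area under the curve (AUC) for the receiver operating characteristic (ROC) curve and by the range of predicted risks". Patients are also divided into fifths of predicted risk: "We will compare the true event rate among the quintile groups". The stated purpose of that last step is to see how well the model separates levels of risk.

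The models are generalized linear mixed models built by stepwise selection. Clinic effects are mentioned earlier in Section 11.3, in the description of the treatment comparison: "The mixed model includes clinic random effects to account for within-cluster correlation". The predictive-model text does not say whether estimated clinic effects form part of a patient's predicted risk.

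Developing and validating these models is a secondary objective (Protocol Summary, objective b; Section 3.1.2.2). Section 15.2 says the models will be released publicly.

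**The concern.** External validation tells a reader that a model was tested on patients from somewhere, or some time, other than its source. A random third of the derivation cohort shares its clinics, systems, calendar period, record extraction and outcome sources with the other two thirds. Someone who takes up the released model and reads that it was externally validated would credit it with evidence that this design cannot supply. The setting makes this matter: Section 5 describes a safety-net system, a private non-profit network, a veterans' system and a Connecticut physician network, and Section 3.2.1 has them ascertain hospitalizations through different sources. Baseline risk may differ between them, and a random split averages over such differences.

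Calibration is a second, separate matter. Univariate screening at p < 0.20, stepwise selection, interactions, splines and recursive partitioning invite overfitting, which typically shows as a calibration slope below 1. A Hosmer-Lemeshow p-value does not estimate that slope, and its result depends on the number of patients.

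**Working it through.** **1. The cohort being split.** The documents give no performance figure for the models, so the figure to reproduce is the cohort size. Section 11.2 inputs: 14% versus 11%, 80% power, two-sided 5%, ICC 0.015, and available patients 4,419, 4,738, 4,175 and 1,093 (total 14,425). On clinics: "The numbers of clinics are 25, 40, 50, and 9 in Parkland, Texas Health Resources, ProHealth, and VA North Texas, respectively", so 124.

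- Unclustered n per arm = [1.960·√(2·0.125·0.875) + 0.842·√(0.14·0.86 + 0.11·0.89)]² / 0.03² = 1,907, or 3,814 in total.
- Design effect per system = 1 + (available patients per clinic − 1)·0.015. With 176.8, 118.5, 83.5 and 121.4 patients per clinic this gives 3.636, 2.762, 2.238 and 2.807. Weighted by available patients: 2.8814.
- 3,814 × 2.8814 = 10,990, against 10,991 stated. The figure reproduces.

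**2. What a random split holds out.** The unit of the split is not named; with no mention of clinics it reads as patients.

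- Validation: 10,991/3 ≈ 3,664. Derivation: about 7,327.
- At the midpoint rate (14% + 11%)/2 = 12.5%, assuming 1:1 allocation, 3,664 × 0.125 ≈ 458 validation patients are hospitalized.
- Enrolled patients per clinic are 134.7, 90.3, 63.6 and 92.6 (Parkland, THR, ProHealth, VA). One third of each is about 45, 30, 21 and 31 in validation.
- With equal clinic sizes m within a system, the expected number of clinics absent from either part is the sum over clinics of (2/3)^m + (1/3)^m ≈ 3 × 10⁻¹⁰.

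Every clinic and all four systems therefore appear in both parts.

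**3. Does this inflate the c-statistic for a new clinic?** Simulation with 124 clinics of the planned sizes, about 12.5% events, and clinic SD on the logit scale √(0.015/(0.125·0.875)) = 0.37 (variance 0.137). The SD of the linear predictor is not in the documents; 0.5, 0.75 and 1.0 were assumed. The table shows mean c-statistic under the random patient split minus that in held-out clinics (150 trials per cell).

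| Predictor SD | Estimated clinic effects used | Fixed effects only |
|---|---|---|
| 0.5 | +0.016 | −0.0001 |
| 0.75 | +0.008 | −0.0019 |
| 1.0 | +0.006 | −0.0002 |

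The Monte Carlo SE of each mean c-statistic is about 0.001, so no value in the last column is distinguishable from zero. Other runs gave 0.705 versus 0.694 at SD 0.75, and gaps of about 0.007 to 0.017 over the SD range, all with clinic effects used. Overall: roughly 0.006 to 0.017 if clinic effects enter, essentially nothing if they do not.

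**4. What Hosmer-Lemeshow detects.** Simulated rejection at the 5% level, 3,664 patients, 12.5% events.

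| True slope | SD 0.5 | SD 0.75 | SD 1.0 |
|---|---|---|---|
| 0.9 | 8% | 14% | 22% |
| 0.8 | 20% | 50% | 77% |
| 0.7 | 44% | 87% | 99% |

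Other runs over the same SDs gave 10 to 21% at slope 0.9 and 23 to 64% at 0.8, inside these ranges. Dependence on sample size is plain: at SD 0.75 an intercept shift of 0.2 is rejected in 86% of samples with 3,664 patients and in 22% with 500. The smaller number is close to the 458 validation patients expected to have an index hospitalization, the population for the 30-day readmission model.

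**The case against.** The strongest reply is that only one word is wrong. Apart from calling the validation external, the plan makes no claim that the models transport. A released model would normally be applied without any trial clinic's random effect, and the predictive-model text uses the mixed model to select variables without saying that clinic effects enter the risks. A reader might infer that reported discrimination will be too high for new clinics. The documents do not support that as an unconditional statement: step 3 shows the gap only where estimated clinic effects are used, and it is about 0.01 even then. This part of the objection stands.

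A reader might also infer that relying on Hosmer-Lemeshow inflates transportability, or that poor calibration would go unseen. Neither follows. The test has no bearing on transportability, and larger miscalibration is often caught (slope 0.7 in 87% of samples at SD 0.75). Observed rates by fifth of predicted risk are most of what a calibration plot needs. But their stated purpose is separation, and neither they nor the c-statistic and range of risks give an intercept or slope.

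Leaving out one system at a time is also debatable: the VA fold has 833 patients, about 833 × 0.125 = 104 hospitalized, which would give imprecise results and too few patients for a useful readmission check.

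What the objection does not rescue is the label. Even if the split were by clinic, both parts would come from the same four systems. The extra clinics mentioned in Section 11.2 are a reserve for enrolment, not a validation set.

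**Conclusion.** The concern holds in a limited form. The plan attributes to its validation a property the design does not have, for a stated secondary objective with a public product. That conclusion needs no modelling assumption beyond reading the random split as the text describes it.

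The size of any optimism in the c-statistic is conditional: roughly 0.006 to 0.017 for a new clinic if clinic effects enter the predictions, essentially none otherwise. It rests on the assumed predictor SDs, on the ICC of 0.015, and on clinics drawn from one common distribution. It therefore says nothing about a new health system, for which no figure can be computed from the documents.

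The calibration gap is separate. That the test yields neither size nor direction needs no simulation; the rejection rates of roughly 8 to 22% at slope 0.9 and 20 to 77% at slope 0.8 depend on the assumed SD. The primary comparison and the sample size are untouched.

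**What to change.** In the predictive-model part of Section 11.3:

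- Describe the validation as internal (split-sample). Alternatively, assign whole clinics to the validation third and describe it as validation in held-out clinics of the same four systems.
- State the unit of the split, and state that validation predictions are computed without the clinic random effect.
- Report calibration intercept, calibration slope and a calibration plot for each model, in place of or alongside the Hosmer-Lemeshow test. Keep the planned c-statistic, range of risks and event rates by fifth.
- Treat leave-one-system-out validation as optional, with the imprecision of the VA fold acknowledged.

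The cost is SAP wording, slightly more analysis and possibly a slightly lower reported c-statistic. No new data are needed: the mixed models already require clinic identifiers.

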13.1 Development of MOP and Training

The main thrust of our quality control and assurance program is to prepare a comprehensive manual of operation with sections specific to each study site and train study site staff in its operations. Study site personnel to be trained are the site PI, the Practice Facilitator and Primary Care Providers at each clinic. The site PI will provide oversight to the conduct of the study at their institution, responsible for recruitment of appropriate staff to serve as Practice Facilitator and engaging PCPs in the clinics randomized to study group. The Practice Facilitator will receive the list of eligible patients along with their PCPs to ensure that the patients are enrolled into the study and provided recommended care through triggering of the Smart Set and following protocol. The PCPs will be primarily responsible for providing recommended care to their eligible patients and determine the level of care for each patient. Training will be provided to these staff by members in person meetings, web-based training and the manual of operation that outlines their expected roles, clinical workflow, opt-out consent and patient follow up. A refresher training course will be provided every three months to ensure compliance with the manual of operations.

13.2 Site Visit

We will develop a timetable to visit the clinics in the study group at least one time per year to observe the clinical workflow and adherence to the MOP. Other visits may occur if requested by clinic staff or if there are concerns with study performance

13.3 Pieces Functionality

We will assure the functionality of our decision support systems software by verifying with each site a sample of patients identified with CKD, Diabetes and Hypertension at the beginning of the implementation period and quarterly thereafter.

13.4 Monitoring Data Quality

The quality of data received from all sites will be reviewed and verified at beginning of the implementation phase and monthly thereafter to ensure problems are identified and corrected in a timely manner

13.5 Routine Progress Reports

We will prepare a monthly progress for each site to include the following:

1. Screening, Recruitment, enrollment and retention
2. Protocol compliance
3. Data quality reports - describe missing, erroneous, and inconsistent data to ensure protocol is followed and deviations are tracked
4. Site monitoring results

14. Ethics/Protection of Human Subjects

14.1 Ethical Standards

This study will follow the highest level of ethical standards. All study staff will be required to train and certify in human subject protection

14.2 Institutional Review Board

The final study protocol will be submitted to UTSW, THR and VA North Texas IRBs for review and approval. Patient recruitment will not occur until the study has been approved by the various IRB. UTSW IRB will serve as the review body for Parkland and ProHealth of Connecticut HCS. Protocol amendments and changes will be submitted to all IRBs and approval must be received prior to implementation.

14.3 Informed Consent Process

This pragmatic clinical trial will offer an opt-out option for any eligible patients in either control or intervention groups. There will be no formal informed consent obtained from each individual patient. The rationale for waiver of informed consent has been carefully reviewed and presented to the IRBs overseeing the study as well as to the federal agencies overseeing the study. The research involves minimal risk to subjects. Both groups including control (standard care group) and intervention will have access to recommended best therapies for treatment of CKD, diabetes and hypertension. In both groups the primary care provider will have the final say on what interventions are implemented for the care of CKD, diabetes and hypertension for their individual patients. The waiver of informed consent will not adversely affect the rights and welfare of participating subjects. This pragmatic trial cannot be performed at all participating

healthcare systems and practice sites without the waiver. As there will be several thousand patients enrolled it would not be logistically possible for coordinators to address the geographic and time limitations to obtain consent from such a large number of participants as to make the trial possible. The risks to patient privacy and data security will be carefully addressed with multiple safeguards as detailed in Section 15 Data Management and Responsibilities. Study subjects will be notified of findings at completion of the study.

As previously mentioned, patients who are in clinics randomized to either control group or intervention group will have an option to opt-out of the study and use of any of their health information. The goal is to give all potential patients the opportunity to know that the study will be carried in their healthcare system and to have the opportunity to decide if they want to participate and if they will allow for their data to be used in the study. Participants will be made aware of the study through various forms including posters and handouts and other media in clinics describing that the study aims to improve care of patients with CKD, diabetes and hypertension by assisting primary care providers to implement the best practices for their care. There will be reference to a phone number and a link to the collaborative website specific to ICD-PIECES so that patients can obtain as much detail as they need to make an informed decision. If a patient does use the opt-out mechanism, the research team will document and track the instances for those patients to remain outside of the study interventions or use of any of their specific data.

14.4 Exclusion of Women, Minorities, and Children (Special Populations)

This study will be conducted in all adults 18-85 years attending the outpatient clinics of the participating Health Care Systems

14.5 Subject Confidentiality

All patient data will be maintained in a secure location. Study data to be obtained will be part of standard information available in the EHR. Access to study data in the EHR, PIECES and study databases for data collection and analysis at UTSW and PHHS will be limited to study personnel and password protected.

14.6 Study Discontinuation

Study participation can be discontinued at any time by patients or their PCPs.

14.7 Future Use of Study Specimens

There will be no study specimens collected for this study. Data will be collected and stored securely. De-identified data will be available for future use as per NIH policies.

15. Data Handling and Record Keeping Informatics Section

15.1 Data Collection

Data capture will be aggregated on a central cloud based (Software-as-a Service) SaaS platform hosting the Pieces™ software. Flat file transfer via SFTP will occur and HL7 based data integration will occur with a site specific selection of the best method to transmit data centrally. In the instance that external approval of data transfer cannot occur, a process of locally matching patient selection criteria on software server with a local firewall will be implemented with a process to allow deidentified data to the SaaS server will be implemented. Access to the central server will be restricted using Secure VPN tunnel with two factor authorization. The Secure Cloud Hosting Environment will be FISMA (**Federal Information Security Management Act of 2002**) compliant.

Hospitalization and Death Outcome Data:

Data requests by the National Association for Public Health Statistics and Information Systems (NAPHSIS) Death index information from the CDC will be obtained after completion of IRB submission for approval and then performed at the termination of the study a single time to obtain death outcomes after enrollment and follow up of planned time period for augmentation of EHR stored death date and death status of inpatient discharge to ascertain mortality outcomes.

Master Patient Index matching to a shared Dallas Fort Worth Hospital Council data set will occur for the THR and PHHS site using the REMPI match system to obtain inpatient hospitalization events throughout the Dallas-Fort Worth area. Patient outcomes within the outside of the Veterans Affairs System will occur with an additional research effort to assess the

feasibility of patient patching between the Veterans Affairs patient index and the DFWHC data to provide additional hospitalization events for veterans outside the VHANTX system.

15.2 Data Management and Reports

Encrypted computers stored in physical secured premise. Patient cohort selection criteria will be preserved in PheKB platform and publically available after the completion of the grant (<https://phekb.org/>). Snapshots of the data elements constituting candidate identification and confirmation will be stored for all patients meeting the candidate definition.

Formats RDBMS using MySQL or Sql Server environment configured to support the data model with access controls overseen by a PCCI Security officer. Deidentified final registry data sets with Safe harbor HIPAA data elements removed will be provided to the final statistics team performing predictive modeling for Aim 3 and final analysis of the planned analysis.

Data aggregation by assigned data analyst from the PCCI under terms of executed Business Associates Agreements between the parties to the grant. Analytic file extracts from the RDBMS will be exported as .csv or tab delimited txt files for additional analysis. Quality Assurance reports will evaluate the distribution and frequency of mapped data elements and validation of the final mapping of the Pieces™ data model will be confirmed with the site coordinators. Periodic reporting on the number of candidate patients per site will be reviewed at least quarterly to monitor for target patient identification consistent with expected patient volumes from power calculations and available on request to the Data Safety Monitoring Board.

Server Data will be backed up on mirrored virtual machines within a partitioned cloud server environment with disaster recovery. RDMBS scripts, stored procedures and Pieces™ platform executables related will be versioned control using Subversion as will data exports to the analytic teams.

DATA VALIDATION:

Annual review of value sets update form the VSAC and HEDIS will be performed to test for the impact of newly released medications or laboratory mappings. Unexpected drop offs in patient identification will also prompt analyst review of site data. Data model and queries will be stored in version control software. Data mappings for the patient selection criteria will undergo dual analyst review with an investigator and site specific revisions will undergo review with the local site investigator. Medication mappings will be explicitly reviewed for name based mappings to target list and route of administration. For example, if an NDC medication code for a blood pressure medication from the current release of RxNorm maps to an inappropriate medication (say an estrogen), inappropriate medications will be removed from final cohort selection.

Laboratory values for LOINC mapped labs will be reviewed for name matching, specimen source and that diagnostic results are in expected ranges by mean, median, maximum, and minimum tables and histograms. Non-numeric text values will be reviewed to generate interpretative keys for all sites with periodic review for text values not mapping to the interpretive key table. For example, if out of range labs reporting changes for HgbA1c from '>12.1' to '>12.3', new text values not seen during the validation phase will be flagged for analyst review. ICD10 conversion dates will be tracked for all institutions and ICD10 crosswalks for inclusion.

Data transfers to federated data store in Pieces system

Data files will be transferred from participating sites via secure FTP at least once weekly to a central database using a standard data model. Local copies of the same data model will be allowed where necessary for data security approvals of participating institutions with entirely local versions of the data model within the VA Internet Firewall planned for initiation of trial activity to expedite information security and privacy concerns. Identical query logic will be used to identify patients on local copies of the Pieces data model. Federated Data Systems using the Pieces system to store research data and perform uniform selection logic. Minimal data transformation steps necessary to standardized date/time formatting and import of data with minimal transformations.

As a condition of the data use agreements signed with ProHealth Physicians, individual elements of the Safe Harbor elements of PHI are encrypted before transmission until they are needed for final data sets linkages for outcome standardization to maximize patient privacy and minimize data loss risk. As a result the data base of candidate and confirmed patients will be mirrored on the ProHealth Corporate Data ware house to allow subsequent on premises identification and generation of worklists.

Data transfers from Pieces system to participating sites

Standardized worklists that represent patients will be transmitted to the clinical sites. Patients with a candidate status and upcoming appointments in the subsequent week will be reported to the practice facilitator for additional follow up confirmatory testing to be arranged. An additional report on confirmed patients with planned visits in the coming week will also be transmitted to the sites. Additional reports on candidate or confirmed patients presenting in the prior week, not reported on the prior report due to new interval data or scheduling changes since the time of the prior report will also be transmitted. Where these data transfers can trigger additional provider notification or worklist integration with the local EHR will be permitted as a site specific IT decisions

Intellectual Property related to the Pieces TM platform is owned by the PCCI. Data definitions and workflows of the cohort selection will be public maintained and associated predictive models for specific aim three will be public released.

Dissemination Methods

Data Sharing Plan and Public Access

We are obliged to share our data within the analytic team of the ICD-Pieces TM trial. The authors will retain the rights to the deidentified final data until the trial is completed. Interested parties will be able to download information about the predictive model from the PCCI website.pccipieces.org.

Short term data storage of transfer files will occur via encrypted drives between password protected encrypted computers.

Roles and Responsibilities

PCCI data analyst

Software:

Statistical analysis planned perform in R Version, Stata MP version

MySQL Server 5.6

Pieces™ Platform Version 2.0

Deidentification Algorithm

DeID (Nematullah et al)

16. Study Administration

